6.2. Recruitment and enrolment

The recruitment of potential subjects will commence only once authorisation has been received from the Regulatory Authorities and the EC.

Table 2: Table showing an overview of the recruitment process

Recruitment method	Coloplast Database	Advertisement	Patient records
Potential subjects	Recruitment will go through Coloplast' own subject database (stoma care users), and a "landingpage" at Coloplast website. Potential subjects are identified by the following searching criteria in the Coloplast database: 
• Has an ileostomy or colostomy	Advertisement i.e. in local shops, sports facilities, local newspapers, social media and stoma associations. The advertisement will state the contact information of relevant Principal Investigator(s) to contact or the web-address for a Coloplast 'recruitment landing page'. A CRO may help by receiving reply	Recruitment from hospitals, home care nurses and outpatient stoma clinics will be via patient visit or screening of subject records kept at the participating sites.

CONFIDENTIAL

	
 • Be at least 18 years of age 	letters-mails and/or answering the phone from interested subjects.	
First contact	
The identified potential subjects will as first contact be sent an Invitation and Reply Letter by mail or email.
 
If a potential subject does not return the reply letter or answer the email, they may be contacted by phone, mail or email to make sure that they have received the approach.
	
Interested subject contact the investigator.
	
The identified potential subjects will be contacted and informed about the investigation by the investigator (via telephone, letter or e-mail).

Second contact	
If potential subjects return the Reply Letter/reply to the email, or have called the investigator as first contact and are interested, the Investigator or delegated site personnel will contact the subjects by phone and give a short introduction to the investigation and go over the inclusion and exclusion criteria.
 
If the subjects do not meet the inclusion criteria or meet the exclusion criteria, this will be registered at the Subject Screening Log.
		
Subject Information Form	
If subjects are eligible and interested in participating, then written information about the investigation (subject information) will be sent to the subjects to ensure that they are given the opportunity to read about the investigation before a possible informational visit, and for them to prepare any possible questions they may have. The subject information provides information to subjects about how to contact the investigator or a representative thereof, or a representative of the sponsor (name, telephone number and e-mail address), if they wish to learn more about the study.
		
First visit Information visit	
If an eligible subject is interested in participating after the first contact, a visit will be arranged in a room reserved to ensure privacy and quiet surroundings at the investigators clinic/department. When arranging the visit, it will be ensured, that the subject has received the Information Form prior to the visit. The subjects will receive both written and verbal information about the possibility of bringing a companion to the informational visit and to any possible subsequent visits.
 
See section 13 for information to be given to the subjects, as well as the informed consent process.
		
Enrolment and inclusion visit (V0)	
The subjects have the right to wait before deciding on participation. If/when the subject decides to participate, he/she will be asked to sign the relevant forms (see section 13). If a subject so desires, and it is certain that it is understood what the investigation entails, and the relevant forms have been signed the subjects are considered enrolled in the investigation.
		

The coordinating clinical manager will have close contact to each site during the recruitment period. The principal investigator, or delegate, at each site will notify the clinical manager of all planned inclusion visits and whenever a subject is enrolled.

When either 48 1-piece or 2-piece users have been included, the inclusion of the respective group, will be paused, to aim for 48 1-piece users and 48 2-piece users to be included.

When the coordinating clinical manager is aware that 96 subjects have been included and randomised, the recruitment will stop. Subjects who have been informed of the investigation and are reflecting on their participation may be included within the first 24 hours hereafter.

CONFIDENTIAL

Recruitment will occur through competitive recruitment in five countries: the Netherlands, Norway, UK, Italy and Germany. The number of countries is chosen to be sure that we can recruit enough subjects within the investigation timelines.

The recruitment period from first subject enrolled to last subject enrolled will be approximately six weeks.

6.3. Subject withdrawal/lost to follow up criteria

The subject is allowed to withdraw from the investigation at any time for whatever reason without any consequences for their future treatment outside the clinical investigation. The Investigator may withdraw a subject from the investigation at any time if they judge it to be the subject's interest.

The investigator must withdraw a subject from the investigation due to:

- Noncompliance with the CIP impacting the scientific integrity of the investigation.
- If subject's safety and wellbeing is compromised by further participation.
- Pregnancy (see section 6.1.3 Pregnancy and breastfeeding)
- Compromise of exclusion criteria 1. or 2. regarding steroid, radio- og chemotherapy

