4.6. Blinding

No blinding will be used in this investigation, as it is not possible to blind the products due to visible differences.

CONFIDENTIAL

5. Investigational products

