7.4. Concomitant treatment

Concomitant treatment, including medication, will be registered in the CRF.

Subjects are not allowed to use barrier cream or barrier film during the investigation.

The skin undergoes major changes during radio- and or chemotherapy, and the skin might get more fragile to product changes. Therefore, subjects are not allowed to receive radio- and/or chemotherapy during the investigation

- low doses chemotherapy is allowed for indications other than cancer

Steroid products on peristomal skin may interfere with the skin condition and use can make the skin more fragile to change of baseplates. Therefore, subjects are not allowed to use topical steroid treatment in the peristomal skin area e.g.

- Low dose systemic steroid treatment (e.g. inhalation) assessed by the investigator are allowed.
- Other systemic steroid treatment (e.g. injection, or tablet) are not allowed.

8. Risk – benefit analysis

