11.1. Statistical design, method and analytical procedures

The primary objective will be evaluated by analysing the primary and secondary endpoints. These analyses are carried out by Medical Affairs, Coloplast A/S and are described in the following. The secondary objective regarding the [REDACTED] will be evaluated out by [REDACTED] and [REDACTED]

All baseline measurements, endpoints and other measurements (see Appendix 1 - Endpoints) will be summarized by descriptive statistics and/or listed. Endpoints and other measurements will be summarized by product, product type (1- or 2-pc) and visit, if relevant. Descriptive statistics for continuous variables are presented with N, Mean, SD (standard deviation), Median, Min and Max), where N denotes the number of subjects contributing with non-missing data. For discrete variables, descriptive statistics are presented with N and percentage, where percentage is based on the total number of subjects/observations with non-missing data.

As it is an exploratory study no adjustment for multiple testing will be applied.

All statistical analyses are made with SAS version 9.4 (SAS Institute Inc., Cary, NC)

Definition of analysis populations

Intention to Treat (ITT), Safety and Per Protocol (PP) populations will be defined at a formal data review meeting just before database lock. As a minimum, the data manager, the clinical manager and the statistician will be involved in the classification of subjects.

The ITT population (full analysis set) will be constituted by all randomised subjects with valid informed consent who have been exposed to at least one product, and with valid information on at least one product with respect to either primary or secondary endpoints.

The PP population will be constituted by a subset of ITT subjects who fulfilled the inclusion/exclusion criteria and did not violate the protocol in a serious way

Any exclusion of subjects from the PP/ITT population must be documented. Invalid individual data points may be omitted from analysis even though the corresponding subject is part of the ITT or PP population. Any exclusion of data points will be documented.

The Safety population will constitute by subjects who have given informed consent.

All statistical analysis will be based upon the ITT and PP population whereas adverse events and Device deficiencies will be assessed based on the safety population.

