12.4. Data retention

The sponsor file must be archived for a minimum period of ten years after the final investigation report has been signed. All site documents must be archived for a minimum period of ten years after the final clinical investigation report has been signed.

13. Amendments to the CIP

No changes in the clinical investigation procedures shall be affected without mutual agreement of the principal investigator and the sponsor. The agreement of the changes must be documented by signing the corresponding clinical investigation plan amendments. All changes must be registered in the Change Log with a rationale.

CONFIDENTIAL

All changes require notification to the EC and the CA (when appropriate). Substantial changes may require approval from the EC and the CA prior to implementation.

14. Deviations from Clinical Investigation Plan

Every effort should be made to avoid deviations from the clinical investigation plan during the conduct of the investigation. The Investigator is not allowed to deviate from the CIP unless under emergency circumstances and to protect the rights, safety and well-being of the subject(s). Deviations must be reported to sponsor and deviations affecting the scientific aspect of the investigation or the safety of the subject (violation) are reported to the EC and regulatory authorities by sponsor if required by national regulations.

For reporting purposes, the sponsor classifies study deviations as major and minor:

Major deviation: Any deviation that may either have an impact on the rights, safety and well-being of the subjects or the scientific outcome of the clinical investigation.

Minor deviation: Any deviation that has no impact on the rights, safety and well-being of the subject or that may impair the scientific outcome of the clinical investigation.

The Investigator should inform the CM/CRA of any deviation, and the implications of each deviation must be reviewed and discussed. If the deviation affect the subject, discussion for a decision on the further participation of the subject should be completed. Any deviation must be documented, stating the reasons, date, actions taken, and the impact for the subject and/or investigation. This documentation must be kept either in the Deviation Log in the Investigator Site File or in the Deviation CRF form, depending on the deviation's relation to either the data collected in the CRF or all other case of any deviations on site.

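### Section 6.3 makes withdrawal mandatory for integrity-affecting noncompliance, with no endpoint collection afterwards, and does not fit sections 4.1, 11.1 and 14

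*Combined protocol and SAP*

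**What the plan says.** Section 6.3 introduces its list with "The investigator must withdraw a subject from the investigation due to". One item is "Noncompliance with the CIP impacting the scientific integrity of the investigation". The section gives no threshold for this item and no one other than the investigator to judge it. Section 4.6 says "No blinding will be used in this investigation", so the investigator knows which product is being worn.

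Three other sections bear on the same situation:

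- **Section 14** defines a major deviation partly by a possible effect on the scientific outcome. It has the investigator inform the sponsor's monitor of any deviation, and then says: "If the deviation affect the subject, discussion for a decision on the further participation of the subject should be completed".
- **Section 4.1** lets a subject who cannot or will not finish a test period go on to the next visit and period and so remain in the trial.
- **Section 11.1** defines ITT as randomised, consenting subjects "exposed to at least one product, and with valid information on at least one product with respect to either primary or secondary endpoints". Per protocol is "a subset of ITT subjects who fulfilled the inclusion/exclusion criteria and did not violate the protocol in a serious way". Both sets are fixed at a data review meeting before database lock, and invalid single data points can be left out while the subject stays in the set.

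Section 7.4 gives a concrete rule that could be broken: "Subjects are not allowed to use barrier cream or barrier film during the investigation". Section 6.1.1 explains that such products could compromise the effect of the new baseplate. The app asks about accessories at each change, and its list includes barrier products (Appendix 1).

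For the period after withdrawal, the readable text describes care and follow-up for adverse events (section 18.5), but no collection of endpoints.

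**The concern.** A site that finds integrity-affecting noncompliance can read three different courses in the plan: withdraw the subject (6.3), discuss and decide (14), or keep the subject and settle the matter in the per-protocol set (11.1). Sites may act differently.

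If 6.3 is followed, the trial loses data that it could have kept. A crossover gets its precision from subjects who contribute to both products, and withdrawal in period 1 removes that contrast for the subject. The primary endpoint comes from the last three weeks of each period, and the readable secondary endpoints are at steady state or end of treatment. A subject withdrawn in the first three weeks of period 1 may therefore have nothing valid on either product, and so may not meet the ITT definition.

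The loss need not be random. Reaching for a barrier product because the skin is sore is plausibly a reaction to the product being worn, and the person who decides on withdrawal knows which product that is. The selection would matter more if the carry-over test led to a first-period-only analysis, because period 1 withdrawals would then act directly on a between-arm comparison.

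**Working it through.** **What is lost, by time of withdrawal**

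| Withdrawal | Data left | ITT status under 11.1 |
|---|---|---|
| Period 1, before steady state | Possibly no valid endpoint data | May fall out |
| Period 1, during or after steady state | First product only | Stays in with valid data |
| Period 2, before steady state | First product; possibly no steady-state data on the second | Stays in with valid data |
| Period 2, during steady state | First product, part of the second | Stays in with valid data |

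**Inputs for the size (section 11.2).** Total SD 1.82; residual share 32%; product-by-subject share 0%; true difference 0.7; 40 subjects per product type, raised to 48 for 20% drop-out; about three weekly maxima per period. The significance level is 5% (section 11.3), taken as two-sided because the test is of a difference from 0.

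**Reproducing Table 4.** Residual variance = 0.32 × 1.82² = 0.32 × 3.3124 = 1.060. With m scores per period and n complete pairs, SE = √(2 × 1.060 / (m × n)), and power comes from a noncentral t with n − 1 degrees of freedom and noncentrality 0.7/SE.

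- m = 1, n = 40: SE = √(2.120/40) = 0.230, noncentrality 3.04, power 84.3% (stated: 85%).
- Sample size for 85% power with m = 1: 41 by the t method. The normal approximation gives 2 × 1.060 × (1.960 + 1.036)² / 0.7² = 38.8, so 39 (stated: 40).

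The plan's figure is therefore reproduced with one score per period.

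**Power with fewer pairs at a difference of 0.7**

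| Complete pairs | m = 1 | m = 3 |
|---|---|---|
| 40 | 84.3% | 99.9% |
| 38 | 82.3% | 99.9% |
| 37 | 81.2% | 99.9% |
| 36 | 80.1% | 99.8% |
| 33 | 76.4% | 99.6% |
| 28 | 68.9% | 98.9% |

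These rows count complete pairs only. A mixed model also uses first-period data from the others. With 33 pairs and 15 such subjects, power at m = 1 is 81.6%, against 78.9% for the 33 pairs alone (both by normal approximation).

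**Possible bias (illustrative).** The documents give no rate of noncompliance or of withdrawal, so the mechanism is an assumption. Take 48 subjects of one product type, a true difference of 0.7, SD 1.82 and a product-by-subject share of 0 to 20%. Suppose that half of those with an early itching score above 5 break a rule and are withdrawn. About 8% are withdrawn, 4-5% have no primary data, and subjects with both products fall from 48 to 44. The estimate, from a mixed-model-type analysis with known variance components, moves from 0.70 to about 0.68-0.70. The number removed depends on the assumed level of early scores; the shift stays small.

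Applied to the 40 planned pairs, the same proportion gives 40 × 44/48 = 36.7, or about 37. That is the 84.3% to 81.2% step in the table.

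**The case against.** There is a good case on the other side, and much of it stands.

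- **ITT membership.** A reader might infer that serious violators leave ITT as well as per protocol. The documents do not support this: valid data on one product are enough for ITT, and nothing says that recorded data are discarded.
- **Second-product data.** A reader might infer that these are never collected. That holds for withdrawal in period 1. After a period 2 withdrawal, whatever was recorded remains.
- **Contradiction with the per-protocol definition.** A reader might infer that 11.1 assumes the opposite of 6.3. It does not. A withdrawn subject with data on one product can be in ITT and out of per protocol, which fits both sections. The point is only that 11.1 already offers a less drastic tool.
- **Triggers.** Sections 6.3, 11.1 and 14 use three different wordings, and none is equated with another. It does not follow that every major deviation or every serious violation forces withdrawal. Barrier products are prohibited, but section 7.4 attaches no withdrawal to their use, and the app is set up to record it.
- **Process.** Section 14 can be read as the way 6.3 is applied, with the monitor involved. Section 4.1 softens the loss for subjects who react badly to one product. Neither section says how it relates to the mandatory wording in 6.3, so the need to reconcile them remains.
- **Size.** The simulated loss, from 48 to 44 pairs, fits inside the drop-out allowance. The step from 40 to 37 places it on top of that allowance.

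The objection does not supply any provision for endpoint data after withdrawal, or a rule on which section governs.

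**Conclusion.** The point holds as an inconsistency with an avoidable loss of data. Section 6.3 mandates withdrawal on a ground that has no threshold, leaves the judgement to someone who knows the product, and is followed by no planned endpoint collection. Sections 4.1, 11.1 and 14 point to milder handling.

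The size is modest. On the one-score-per-period basis, power falls by about three percentage points (84.3% to 81.2%). With the three weekly scores that section 11.2 expects, the loss is negligible. The shift in the estimate is at most about 0.02 on a difference of 0.70 under the assumed mechanism. A reader might infer a material bias from selective withdrawal by an unblinded investigator. The documents give no rate from which to show it, and the illustrative calculation does not produce it. A higher or more product-dependent rate would change the figures, so the size is not established in either direction.

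Label: cheap improvement, low severity.

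**What to change.** Reconcile the noncompliance item in 6.3 with sections 4.1, 11.1 and 14, so that a site can tell which applies. Add to 6.3 that noncompliance alone does not end endpoint data collection where the subject agrees: it is logged as a deviation under section 14, and the scheduled visits and app entries continue. Add to 11.1 that all data recorded for such subjects stay in ITT, and that their per-protocol status is decided at the data review meeting.

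The grounds of safety, pregnancy, and steroid, radio- or chemotherapy are untouched. The change concerns data collection only. Whether a subject goes on using the assigned product is for the sponsor to settle when the sections are reconciled, and no rule on that is proposed here.

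The cost is about two sentences. The downside is that ITT will contain some data from subjects who broke a rule, which the per-protocol analysis is there to check.

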6.3.1. Screening failures

Screening failures are considered subjects that have signed the informed consent form and been included based on in- and exclusion criteria, but not yet randomised.

Subjects that have signed the informed consent form but fails to comply with the in- and exclusion criteria are also considered screening failures.

Screening failures can be replaced by a new subject.

6.4. Point of enrolment

A subject is considered enrolled in the investigation when the written informed consent is obtained. The expected duration for each subject is described in section 4.1.

6.5. Subject Identification and confidentiality

Subjects will be identified on the electronic CRF (eCRF) and any other document transmitted to the sponsor by the principal investigator, or delegate, by a unique identification number (subject number) only.

Data entered on the eCRF are confidential and will only be available to the sponsor (including sponsor delegates), members of data management teams, the statistician, Medical Advisor or Data Safety and Monitoring board, and if requested to regulatory authorities.

The principal investigator for each clinical investigation site will maintain as part of the investigator site file a list identifying all subjects entered in the clinical investigation (Subject Identification Code and Enrolment List). This list is confidential to all others than the Principal Investigator, or delegate at the site.

CONFIDENTIAL

7. Procedures

7.1. Clinical investigation-related procedures

Before initiation of the clinical investigation, sponsor must be provided with key personnel signed and dated curriculum vitae (not more than two years old) to verify their qualifications. Key site personnel are those, who treat or evaluate subject data in the clinical investigation. Also, the sponsor will ensure that all site personnel are trained in the investigation procedures, how to complete the CRFs, procedure for reporting an adverse event or serious adverse event (how, when, to whom), and who to contact in case of emergency related to the investigational products.

See section 7.2 Flow-chart for a more detailed overview of the clinical investigation-related procedures at visits, phone visits and at product/baseplate change.

7.1.1. Site visits

Visit 0 (Inclusion visit)

If a potential subject is interested in participating after the first contact, a visit (visit 0) will be arranged in a room reserved to ensure privacy and quiet surroundings at the investigators clinic/department. When arranging the visit, it will be ensured, that the subject has received the Subject Information Form prior to the visit. The subjects will receive both written and verbal information to ensure that the subject understands what was read and explained and can freely agree to participate in the investigation. The subject will, beforehand, also be informed about the possibility of bringing a companion to Visit 0 and to any possible subsequent visits. During the visit the principal Investigator, or delegate, will provide oral information about the investigation based on the Subject Information Form. The subject has the right to wait before deciding on participation.

If/when subjects decide to participate, they will be asked to sign the Informed Consent Signature Form. Hereafter, relevant female subjects will be asked to give a urine sample for a pregnancy test. The sample will be destroyed right after the test. If a subject so desires, and it is certain that it is understood what the investigation entails, and the relevant form has been signed the subjects are considered enrolled in the investigation. Enrolled subjects that are deemed eligible per the inclusion/exclusion criteria are allocated a subject number.

Visit 0 and visit 1 can be combined.

Test visits (V1, V2 and V3)

During test visit 1, the subject will be randomised to either treatment Arm A or Arm B and will be allocated a randomisation number. Hereafter the baseline questions will be completed by the Principal Investigator, or delegate. The subjects will be introduced to the clinical trial app and how to complete the questionnaires and take photos.

At test visit 1 and 2 investigational products (CE marked comparator products or non-CE marked Investigational Product) will be handed out according to the randomisation. The subject will only be informed about which product to wear in the upcoming period. At the visits the subjects will be trained according to the IFU, in preparation of the product (e.g. hole size), preparation of skin before application (e.g. cleaning and wiping), application of the product (e.g. correct position and applying pressure to the baseplate), removal of product and storage of the product.

At each test visit the Principal Investigator, or delegate, will assess the skin and complete questionnaires about the subject's peristomal skin condition and ask the subject about stoma behaviour since last visit/call. The

CONFIDENTIAL

subject will, at each test visit, complete questionnaires about e.g. skin condition, stoma behaviour, leakage and quality of life. Additionally, the principal investigator, or delegate, will take a photo of the peristomal skin, for assessment of changes in peristomal skin condition from Test visit 1 to Test visit 2, and from test visit 2 to test visit 3.

At test visit 2 and 3 the Principal Investigator, or delegate, will also complete questionnaires about changes in peristomal skin condition. The subject will also complete questionnaires about changes in peristomal skin conditions, feeling of security and handling of the product.

It must be ensured that the subject sits alone in a room reserved to ensure privacy and quiet surroundings and is not disturbed when the completing the questionnaires at the visit.

